### **Reporting of Suspected or Known Unintended Exposure to Talimogene Laherparepvec and Herpetic Illness in Close Contacts and Healthcare Providers**

Potential or known unintended exposure to talimogene laherparepvec, and any related suspected signs or symptoms in a subject's close physical contact, household member, caregiver, or healthcare provider will be reported. If consent of a close contact or healthcare provider is provided, the exposed individual may be asked to have a swab taken to evaluate for the presence of talimogene laherparepvec in suspicious lesions. The positive qPCR for talimogene laherparepvec DNA detection from suspicious lesions will be reported. These individual cases in secondary contacts will be reported with separate ID numbers to distinguish them from subjects' data. More details will be provided in a program-level SSAP for unintended exposure to talimogene laherparepvec.

### **Disease-related Events**

A sensitivity analysis of treatment-emergent adverse events will be conducted that considers any disease-related events as an adverse event if the disease-related event was reported in the study for any subject as a treatment-emergent adverse event. Subject incidence of disease-related events will be summarized for all treatment-emergent disease-related events, fatal disease-related events, serious disease-related events, disease-related events leading to withdrawal from study drug, and significant disease-related events will be provided separately as a sensitivity analysis.

#### **9.6.3 Laboratory Test Results**

Lab-defined lower and upper limits of normal ranges will be used for chemistry, hematology, coagulation, immunology, and toxicology laboratory tests. NCI Common Toxicity Criteria (CTC) version 4.03 grading will be used. Laboratory results will be summarized with descriptive statistics at baseline and selected time points. Grade shifts in important laboratory results from baseline to worst on-protocol value will be presented. The incidence of post-baseline laboratory abnormalities will be provided.

#### **9.6.4 Vital Signs**

Descriptive analyses of temperature, blood pressure, respiratory rate, and heart rate will be conducted at baseline and selected time points.

#### **9.6.5 Physical Measurements**

Descriptive analyses of temperature, blood pressure, respiratory rate, and heart rate will be conducted at baseline and selected time points.

### **9.6.6 Exposure to Investigational Product**

In Part 1, descriptive statistics will be produced to describe the exposure to Amgen investigational product talimogene laherparepvec and non-Amgen investigational product pembrolizumab by cohort/group (non-HCC vs HCC vs overall). Subjects in **cohort 1** to cohort 4 will be exposure to monotherapy treatment.

In Part 2, descriptive statistics will be produced to describe the exposure to Amgen investigational product talimogene laherparepvec and non-Amgen investigational product pembrolizumab by tumor type/group (non-HCC vs HCC vs overall).

Summary statistics for exposure to talimogene laherparepvec or/and pembrolizumab, including total doses administered, total volume administered, treatment visits with IP MTV  $\leq$  4ml, treatment visits with MTV volume  $>$  4ml, duration from the first to the last administration of talimogene laherparepvec, and the average volume received by subject per visit will be provided and will be separated by the first (concentration of  $10^6$  PFU/ml) and subsequent doses. The subject incidence rate and reasons for IP delays, missed treatment, and withdrawal will be tabulated.

### **9.6.7 Exposure to Other Protocol-required Therapy**

Summary statistics for subjects in the Full Analysis Set who undergo on-protocol surgery including any surgery/procedure performed, type of procedure, and intent of surgery (e.g., palliative) will be provided.

### **9.6.8 Exposure to Concomitant Medication**

[figure not shown]
Concomitant medications include all medications received during the treatment period other than the protocol drug. The number and proportion of subjects receiving any concomitant medications during the treatment period will be summarized by preferred term as coded by the World Health Organization Drug (WHO DRUG) dictionary. A list of selected medications and their groupings are provided.

## **9.7 Other Analyses**

### **9.7.1 Analyses of Pharmacokinetic or Pharmacokinetic/Pharmacodynamic Endpoints**

A separate SSAP will be prepared for the exploratory endpoints and this analysis may be reported separately.

Enter Analyses of Health Economic Endpoints

**10. Changes From Protocol-specified Analyses**

N/A

**12. Prioritization of Analyses**

N/A

**13. Data Not Covered by This Plan**

N/A

**14. Appendices**

**Appendix A. Reference Values/Toxicity Grades**

CTCAE v. 4 grading scale will be used for adverse event coding:

1 – Mild

[figure not shown]
2 – Moderate

[figure not shown]
3 – Severe

4 – Life-threatening

5 – Death

Enter Appendix Concomitant Medications

### Appendix C. Wilson's Score Method with Continuity Correction in Calculating the 95% Confidence Intervals for Difference in 2 Independent Proportions

The following formula of interval estimation is extracted from Newcombe 1998 paper:

Assuming

$$X_i \stackrel{i.i.d.}{\sim} \text{Bernoulli}(\pi_1), \text{ where } i = 1, 2, \dots, m.$$

$$Y_j \stackrel{i.i.d.}{\sim} \text{Bernoulli}(\pi_2), \text{ where } j = 1, 2, \dots, n.$$

$$\theta = \pi_1 - \pi_2$$

$$\hat{\pi}_1 = \sum_{i=1}^m x_i / m = a / m .$$

$$\hat{\pi}_2 = \sum_{j=1}^n y_j / n = b / n .$$

Then the  $100(1 - \alpha)\%$  confidence interval for  $\hat{\theta} = \hat{\pi}_1 - \hat{\pi}_2 = a / m - b / n$ , with continuity correction is

$$\delta = \sqrt{\{(a / m - l_1)^2 + (u_2 - b / n)^2\}}$$

$$\varepsilon = \sqrt{\{(u_1 - a / m)^2 + (b / n - l_2)^2\}}$$

$l_1$  and  $u_1$  delimit the interval  $\{\pi_1 : |\pi_1 - a / m| - 1 / (2m) \leq z_{1-\alpha/2} \sqrt{\pi_1(1-\pi_1) / m}\}$  and

$l_2$  and  $u_2$  delimit the interval  $\{\pi_2 : |\pi_2 - b / n| - 1 / (2n) \leq z_{1-\alpha/2} \sqrt{\pi_2(1-\pi_2) / n}\}$ .

## Appendix D. Technical Detail and Supplemental Information Regarding Statistical Procedures and Programs

### D.1 Sample Posterior Probability Calculation

```
%macro baybls (as      = ,      /* Standard beta a      */
              bs      = ,      /* Standard beta b      */
              ce      = ,      /* Exp beta precision    */
              delta   = ,      /* Exp mean - std mean  */
              n       = ,      /* 1-arm study sample size */
              x       = ,      /* # responders          */
              dmin    = 0,     /* Plot delta min       */
              dmax    = 30,    /* Plot delta max       */
              dby     = 5,     /* Plot delta increment  */
              alpha   =0.10 /* 100-alpha credible intervals */);
```

```
*** Prior distributions for standard and experimental ***;
```

```
data _null_;
```

```
  * Prior for standard (s) ;
```

```
  as = &as;
```

```
  bs = &bs;
```

```
  ms = as/(as+bs);    * mean of single agent ;
```

```
  Bsc = beta(as,bs);
```

```
  * Prior for experimental (e) ;
```

```
  ce = &ce;          * Concentration parameter (sample size) ;
```

```
  delta = δ    * Absolute rate increase over standard ;
```

```
  ae = ce*(ms + delta/2);
```

```
  be = ce*(1 - (ms + delta/2));
```

```
  me = ae/(ae+be);    * Mean of experimental ;
```

```
  call symput('ms',trim(left(put(ms,6.4))));
```

```
  call symput('Bsc',Bsc);
```

```
  call symput('ae',trim(left(put(ae,6.4))));
```

```
  call symput('be',trim(left(put(be,6.4))));
```

```
  call symput('me',trim(left(put(me,6.4))));
```

```
run;
```

```
*** Experimental posterior distribution ***;
```

```
data combo_post;
```

```
  ae_p=&ae+&x;
```

```
  be_p=&be+&n-&x;
```

```
  me_p=ae_p/(ae_p+be_p);
```

```
  * 95% credible interval for experimental ORR ;
```

```
  cr_ll=betainv(0.025,ae_p,be_p);
```

```
  cr_ul=betainv(0.975,ae_p,be_p);
```

```
  call symput('ae_p',trim(left(put(ae_p,6.2))));
```

```
  call symput('be_p',trim(left(put(be_p,6.2))));
```

```
  call symput('me_p',trim(left(put(me_p,6.4))));
```

```
run;
```

```
proc print data=combo_post noobs;
```

```
  var ae_p be_p me_p cr_ll cr_ul;
```

```
  title1 "Prior standard Beta(&as,&bs), mean=&ms; Prior experimental  
Beta(&ae,&be), mean=&me";
```

```
  title1 "Experimental posterior ORR 95% Credible Region";
```

```
  title2 "N=&n, X=&x";
```

```
run;
```

```

*** Plot of experimental prior and posterior ***;
data plot;
  * Prior ;
  lab='Prior      ';
  Bec = beta(&ae, &be);
  do x=0 to 1 by .001;
    if x le 1 then f=(x**(&ae-1)) * ((1-x)**(&be-1))/Bec;
    output;
  end;
  * Posterior ;
  lab='Posterior';
  Bec_p = beta(&ae_p, &be_p);
  do x=0 to 1 by .001;
    if x le 1 then f=(x**(&ae_p-1)) * ((1-x)**(&be_p-1))/Bec_p;
    output;
  end;
run;

axis1 minor=none value=(h=2.25) length=65
  label=(a=90 h=2.5 'Beta Density');
axis2 label=(h=2.5 'Objective Response Rate') minor=none value=(h=2.25)
  order=(0 to 1 by .1);
symbol1 v=none w=2 i=spline line=1 c=blue;
symbol2 v=none w=2 i=spline line=2 c=black;
legend1 label=none value=(h=2.25 j=1) down=2 mode=share
  position=(inside top middle);
title; footnote;

data _null_;
  set combo_post;
  call symput('cr_ll', trim(left(put(cr_ll, 6.2))));
  call symput('cr_ul', trim(left(put(cr_ul, 6.2))));
run;

filename gf "&prefix.Exp_prior_post.emf";
proc gplot data=plot;
  plot f * x = lab
    / vaxis=axis1
      haxis=axis2 noframe
      legend=legend1;
  note h=2.25
    move=(70,73) 'Prior'
    move=(70,70) "Beta (&ae, &be)"
    move=(70,67) "Mean = &me"
    move=(70,61) 'Posterior'
    move=(70,58) "Beta (&ae_p, &be_p)"
    move=(70,55) "Mean = &me_p"
    move=(70,52) "95% CR: &cr_ll, &cr_ul";
run; quit;

*** Calculate posterior prob. exp ORR >= std ORR + delta ***;
%macro suba;
data inc;
  retain rec 0;
  do c=&dmin to &dmax by &dby;
    d=c/100;
    rec+1;
    output;
  end;
run;
%macro n_obs(ds      =, /* Dataset          */
             whr     =, /* Where clause       */
             n_var   = /* Name of output variable */ );

```

```

%global &n_var;
data n_obs_;
  set &ds
    %if &whr ne %then %do;
      (where=(&whr))
    %end; ;
data _null_;
  dsid=open("n_obs_");
  nobss=attrn(dsid,"nobs");
  call symput("&n_var",trim(left(put(nobs,8.0))));
run;
%mend n_obs;
%n_obs(ds=inc,whr=&n_var=n_obs);

%do i=1 %to &n_obs;
  data _null_;
    set inc (where=(rec=&i));
    call symput('d',trim(left(put(d,6.4))));
    call symput('ul',trim(left(put(1-d,6.4))));
  run;

  proc iml;
    start fun(x);
      v = (1-probbeta(x+&d,&ae_p,&be_p)) * (x**(&as-1)) * ((1-x)**(&bs-
1))/&Bsc;
      return(v); finish;

    * Prob. Exp ORR >= Std + delta ;
    lim = {0 &ul};
    call quad(pr,"fun",lim);

    create p1 from pr [colname='pr_d']; append from pr; close p1;
    quit;
    data t; set p1; d=&d+0; n=&n+0; x=&x+0; rate=x/n; run;

    %if &i=1 %then %do;
      data prs; set t; run;
    %end;
    %else %do;
      data prs; set prs t; run;
    %end;
  %end;

proc print data=prs noobs label split='\';
  var d pr_d;
  title 'Posterior probability Exp ORR >= Std ORR + delta';
  label d='Delta' pr_d='Prob\Exp-Std ORR\>=Delta';
  format pr_d 8.3;
run;
%mend suba;
%suba;

*** Posterior mean and equal-tail credible interval for delta ***;
data dat;
  arm=2; n=&n+0; y=&x+0;
run;

ods output PostIntervals=PostInt PostSummaries=PostSum;
*ods listing gpath="&gpath" image_dpi=150;
*ods graphics on / imagefmt=wmf imagename="Post" reset=index width=4.5in
height=3in;
proc mcmc data=dat outpost=post
  seed=11810 nbi=1000 mintune=4 maxtune=24 ntu=2000
  nmc=50000 thin=1

```

```

monitor=( _parms_ pe_pc) diagnostics=all
stats(alpha=&alpha)=all
/*plots=(trace autocorr density)*/;

parms pc pe;
prior pc ~ beta(&as, &bs);
prior pe ~ beta(&ae, &be);

pe_pc = pe - pc;

if arm=1 then llike=lpdfbin(y,n,pc);          * logL of standard *;
else if arm=2 then llike=lpdfbin(y,n,pe);    * logL of experimental *;

model general(llike);
run;
*ods graphics off;

data post;
  merge postint (where= (parameter='pe_pc') keep=parameter alpha CredibleLower
CredibleUpper)
  postsum (where= (parameter='pe_pc') keep=parameter mean);
  by parameter;
  n=&n+0; x=&x+0; rate=x/n;
data _null_;
  call symput('cr',trim(left(put(100-&alpha*100,8.0) )));
run;
proc print data=post noobs label;
  var parameter mean alpha CredibleLower CredibleUpper;
  title "Delta &cr% Credible Interval";
run;
%mend bayb1s;

```

## D.2 Two Stage Confidence Interval by [Atkinson and Brown](#)

```

%macro cal (n1=10, /*first stage sample size*/
           n, /*total number of subjects enrolled*/
           c1=2, /*critical value for rejection in the first stage */
           c=, /*the total number of responses observed */
           alpha=0.05 /*100-alpha credible intervals*/);

data m1;
n1=&n1;
n2=&n-n1;
c1=&c1;
do theta =0 to 1 by 0.0001;
  do j= c1 to &c;
    if j=c1 then do; y1=cdf('BINOM', c1, theta, n1);
      output;
    end;
    else do;
      do i=c1+1 to j;
        y1=pdf('BINOM', i, theta, n1)*pdf('BINOM', j-i, theta, n2);
          output;
        end;
      end;
    end;
  end;
run;

proc sql ;
create table sum as
select distinct n1, n2, c1, theta, sum(y1) as sum1
from m1

```

```
group by theta
having calculated sum1 >= &alpha/2
order by theta desc
;
create table sum2 as
select distinct n1, n2, c1, theta, sum(y1) as sum2
from m1
where j ne 5
group by theta
having calculated sum2 <= (1-&alpha/2)
;

data _null_;
set sum ;
if _n_=1 then call symput ("Upper_Limit", theta);
run;

data _null_;
set sum2 ;
if _n_=1 then call symput ('Low_Limit', theta);
run;

%put &Low_Limit &Upper_Limit;
%mend;
```

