### **Sample Size Considerations for Part 2**

The recommended phase 2 dose from Part 1 (RP2D) for non-HCC (Group A) and HCC (Group B) will be evaluated in Part 2 independently for each tumor type arm for the combination of talimogene laherparepvec with systemic pembrolizumab. Subjects that initiate treatment at the corresponding RP2D in Part 1 will not be included in the Part 2 efficacy analysis according to their respective tumor type arm.

The primary objective in Part 2 for each tumor type arm will be to evaluate the ORR per modified irRC-RECIST with a minimum potential follow-up of at least 29 weeks. The null hypothesis (H0) for each tumor type is an ORR  $\leq$  10% which, if true, would not warrant further evaluation in contrast to the alternative hypothesis (H1) of an ORR  $\geq$  40%.

[figure not shown]
The following 2-stage design will be used to reject H0 at a  $\leq$  2.5% 1-sided significance level. The efficacy analysis will be based on the Full Analysis Set in part 2 only. A cumulative total of 10 subjects will be treated in Stage 1 and enrollment is planned to stop. If there are 2 or more responders (PR or CR no confirmation is needed), then a total of 11 additional subjects will be treated in Stage 2; otherwise, H0 will be accepted

and enrollment will be permanently discontinued. If the required number of responders to continue to Stage 2 is observed before the end of Stage 1 enrollment, then enrollment will not be suspended.

H0 will be rejected after Stage 2 if there are  $\geq 6$  responders (with confirmation) in 21 treated subjects, ie, the observed ORR is  $\geq 28.6\%$ . In the event precisely 21 subjects are not included in the analysis in total, H0 will be rejected if the lower limit of the 95% exact binomial CI is  $> 10\%$  ([Atkinson and Brown, 1985](#)) (see code fragment in [Appendix D.2](#)). If exactly 10 and 11 subjects are included at Stage 1 and 2, respectively, the design achieves a 1-sided 1.3% significance level, 88.4% power, and the probability of stopping at Stage 1 if H0 (H1) is true is 73.6% (4.6%).

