#### **7.1.3 Interim Futility Analysis (Part 2)**

One interim efficacy futility analysis will occur after 10 subjects have been treated with the combination in Part 2 by tumor type and have had an opportunity to be followed up for at least 20 weeks. Enrollment will be suspended for the specific tumor type arm pending the outcome of the interim analysis. If there are 2 or more responders (CR or PR confirmation not required), then a total of 11 additional subjects will be treated; otherwise, further enrollment of the tumor type will be permanently discontinued. If at least 2 responders are observed by the enrollment of the 10th treated subject, then enrollment will not be suspended. The database will be cleaned, and a database snapshot will be used in the analysis.

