#### **8.7 Validation of Statistical Analyses**

Programs will be developed and maintained, and output will be verified in accordance with current risk-based quality control procedures.

Tables, figures, and listings will be produced with validated standard macro programs where standard macros can produce the specified outputs.

The production environment for statistical analyses consists of Amgen-supported versions of statistical analysis software; for example, the SAS System version 9.4 or later.

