**Table 9-1. Primary Efficacy Endpoint Summary Table**

Endpoint	Primary Summary and Analysis Method (Specify Analysis Set if FAS is Not Used)	Sensitivity Analysis
Part 2: • ORR per modified irRC-RECIST with intratumoral injection of talimogene laherparepvec into cutaneous, subcutaneous, lymph node, or liver tumors in combination with systemic IV administration of pembrolizumab separately by tumor type.	The 2-stage design will be used to evaluate the ORR per the modified irRC-RECIST. The null hypothesis of a 10% ORR for a given tumor type that continued to Stage 2 will be rejected if an exact binomial 95% CI for the ORR is above 10% (Atkinson and Brown, 1985).	N/A

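### The SAP Appendix D.2 confidence-interval code uses the wrong Stage 1 boundary and a fixed count of 5, so Stage 2 arms of 11 to 20 subjects would reject H0 one or two responders too early

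*SAP*

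**What the plan says.** SAP 3.2 sets a 10 + 11 two-stage design for each tumor-type arm, with H0: ORR ≤ 10%, H1: ORR ≥ 40% and a one-sided level of at most 2.5%. SAP 7.1.3 gives the Stage 1 rule: "If there are 2 or more responders (CR or PR confirmation not required), then a total of 11 additional subjects will be treated"; otherwise the arm closes. So the arm stops at 0 or 1 responders in 10. With exactly 21 subjects, H0 is rejected at 6 or more confirmed responders.

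For other totals SAP 3.2 switches rule. "In the event precisely 21 subjects are not included in the analysis in total", rejection requires the lower limit of the 95% exact interval to exceed 10%, and the reader is told to "see code fragment in [Appendix D.2". Table 9-1 states the interval rule generally: the null "for a given tumor type that continued to Stage 2 will be rejected if an exact binomial 95% CI" lies above 10%.

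SAP 3.2 also reports a one-sided level of 1.3%, power of 88.4%, and that "the probability of stopping at Stage 1 if H0 (H1) is true is 73.6% (4.6" (the last figure is also a percentage).

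The Appendix D.2 macro sets "c1=2, /*critical value for rejection in the first stage". Its data step takes the binomial CDF at c1 as the stopped probability and starts the continuing paths at c1 + 1. The upper-limit query sums every term up to the observed count c. The lower-limit query sums the same terms except j = 5, whatever c is. In the macro header the total sample size is printed as "n, /*total number of subjects enrolled", without an equals sign, after a keyword parameter.

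**The concern.** The code departs from the design in two places.

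1. **Stage 1 boundary.** In this code c1 has to be the largest Stage 1 count at which the arm stops. The design makes that 1. With c1 = 2, an arm with exactly 2 Stage 1 responders is counted as stopped although the plan continues it.
2. **Excluded term.** An exact lower limit at an observed total c is built on the probability of fewer than c responders, so the term at c must be left out. The code always leaves out 5. For c below 5 nothing is left out; for c above 5 the wrong term is. Only c = 5 is handled as intended.

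This is the only implementation the SAP cites for the primary-endpoint decision when an arm does not total 21. If it is used, an arm could be declared successful with fewer responders than the written rule requires.

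**Working it through.** **Inputs.** n1 = 10, continue at ≥ 2, p0 = 10%, p1 = 40%, reject at ≥ 6 of 21 (SAP 3.2); alpha = 0.05, i.e. 0.025 per tail, and a grid of 0.0001 for the response rate (Appendix D.2). X1 and X2 are the Stage 1 and Stage 2 responder counts.

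**Step 1: reproduce the plan's figures.** The rejection probability is the sum over i ≥ 2 of P(X1 = i) × P(X2 ≥ 6 − i), with 10 and 11 subjects. This gives 1.33% at p = 10% and 88.4% at p = 40%. P(X1 ≤ 1) is 73.6% at 10% and 4.6% at 40%. All match SAP 3.2. Stopping at ≤ 2, as the code does, would give 93.0% and 16.7%, so the SAP's own stopping probabilities show that the boundary is 1.

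**Step 2: one case by hand, 4 responders in 20.** The macro's lower limit is the smallest response rate at which its sum is ≤ 0.975. At a rate of 10% the printed logic sums:
- P(X1 ≤ 2) = 0.9298
- total 3: 0.0574 × 0.3487 = 0.0200
- total 4: 0.0574 × 0.3874 + 0.0112 × 0.3487 = 0.0261

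The sum is 0.9759, above 0.975, so the limit lies just above 10% (10.1%) and H0 is rejected. The correct sum is P(total ≤ 3) with stopping at ≤ 1, which is 0.8987. The limit is therefore below 10% (6.3%) and H0 is not rejected.

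**Step 3: all totals from 11 to 20.** The logic was ported to Python, reading n as a keyword parameter, and run as printed and with both errors corrected. Type I error is at ORR 10%, with the true Stage 1 rule (≥ 2 of 10) and the same responses counted at both stages.

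| n | Cut-off, printed | Cut-off, correct | Type I error, printed | Type I error, correct |
|---|---|---|---|---|
| 11 | 3 | 4 | 8.96% | 1.85% |
| 12 | 3 | 5 | 10.70% | 0.43% |
| 13 | 4 | 5 | 3.38% | 0.65% |
| 14 | 4 | 5 | 4.27% | 0.92% |
| 15 | 4 | 5 | 5.21% | 1.25% |
| 16 | 4 | 5 | 6.18% | 1.65% |
| 17 | 4 | 5 | 7.17% | 2.10% |
| 18 | 4 | 6 | 8.17% | 0.62% |
| 19 | 4 | 6 | 9.16% | 0.82% |
| 20 | 4 | 6 | 10.13% | 1.06% |

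The plan counts unconfirmed responses at Stage 1 and confirmed ones at the end. Removing the Stage 1 gate altogether gives an upper bound: 3.4%–13.3% printed, 0.4%–2.2% correct.

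**Step 4: how often the two versions disagree.** They differ at 3 responders (n = 11), 3 or 4 (n = 12), 4 (n = 13–17), and 4 or 5 (n = 18–20). Given that an arm passed Stage 1, the chance of such a total is 10%–39% at a true ORR of 10% and 24%–57% at 20%.

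**Step 5: totals of 21 and above.** The cut-offs agree (6 at n = 21–24, 7 at n = 25), but the limits do not. Lower limits, printed against correct: 6/21, 10.7% against 11.5%; 10/21, 11.3% against 25.7%; 14/21, 11.3% against 43.0%. Upper limits: 5/21, 55.9% against 49.1%; 6/21, 56.9% against 52.9%.

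**Step 6: correcting only one error.**
- Only the 5 corrected: type I error stays at 2.6%, 2.6%, 3.2% and 3.8% at n = 12, 18, 19 and 20, and is 2.8% at n = 25.
- Only c1 corrected: 9.0% at n = 11, 2.6% at n = 12, 3.4%–7.2% at n = 13–17, and no total rejects at n = 20–25, including 21.

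**The case against.** The written rule in SAP 3.2 and Table 9-1 is correct, and the appendix is offered as supplementary code. SAP 8.7 says "output will be verified in accordance with current risk-based quality control procedures", which might catch both errors. c1 is a default that a programmer can override. As printed, the header places a positional parameter after a keyword one, which SAS does not accept, so someone may have to edit the macro before it runs at all; SAS was not available to test this. The equals sign may have been lost when the PDF was read, so it is not counted as a third error. Other lines in Appendix D also look garbled, so one could ask whether the 5 is genuine. Nothing points to a misread there. If it were one, c1 = 2 alone would still exceed 2.5% at n = 12 and 18–20.

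The practical reach is uncertain. Protocol 3.3 gives 53 Part 2 subjects over six arms, which fits with no arm above 10 (6 × 10 = 60). If three arms have 11 or more, at least one is below 21 (3 × 21 = 63). If four do, all four are (21 + 3 × 11 = 54). These are conditional statements, not evidence that any arm is affected.

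Two refinements stand. A discordant result is a rejection that the written rule would not make; it is a type I error only if the true ORR is 10% or less. And the macro returns no lower limit for 0 or 1 confirmed responders, before or after correction. Such a total never rejects H0, but it can occur because Stage 1 counts unconfirmed responses.

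**Conclusion.** The concern holds. The code contradicts the design it is meant to implement, in two places that can be checked against the SAP's own stopping probabilities and the definition of an exact lower limit. For arms of 11 to 20 subjects it sets the cut-off one or two responders too low, and type I error exceeds the stated 2.5% at every one of those sizes: 3.4%–10.7% instead of 0.4%–2.1%. All discordant decisions are in the direction of rejecting H0. At 21–25 subjects the decision is right but the reported interval is wrong, grossly so at high response counts.

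These figures assume exactly 10 subjects in Stage 1, n read as a keyword parameter, and the same responses counted at both stages. The number of affected arms is unknown and may be zero. The correction should still be made before the primary analysis, because this fragment is what the SAP names for the decision.

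**What to change.** Make these edits to Appendix D.2 together, since either logic edit alone leaves wrong decisions:

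- set c1 = 1 and describe it as the largest Stage 1 count at which the arm stops;
- in the lower-limit query, exclude j = &c instead of 5;
- declare the sample-size parameter as `n=,` if the equals sign is really missing;
- state what is reported for 0 or 1 confirmed responders, where the macro yields no lower limit.

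Print validation values beside the code: lower limits of 11.5% for 6/21, 8.6% for 5/21 and 6.3% for 4/20. The 6/21 case also diagnoses a partial repair: 9.2% means only c1 was corrected, 12.3% means only the 5 was, and 10.7% means neither was.

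The cost is two logic edits, possibly one header character, and a few lines of text in the SAP. No patients and no protocol change are involved.
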